8.5 Monitoring and Safety Guidelines

The team will assess safety on routine monitoring conference calls which will occur at least every 4 weeks for Cohorts 1 and 2. Safety analyses will be performed at full accrual to Cohort 1, at interim analysis when 8 participants have been accrued to Cohort 2 and at full accrual to Cohort 2, evaluating whether the safety guidelines specified in Section 8.52 have been met. For dose finding purposes, infants who have been excluded from the PK analyses, due to evidence of problematic exposure to the study medication, will also be excluded from evaluation of the safety guidelines.

The attribution of relationship of serious adverse events to study drug for the purposes of employing the start, stop and pause rules will be by consensus among the site investigator, study team (which includes representatives from Merck) and DAIDS medical officer; if unanimous agreement between them cannot be established, the attribution made by the majority of these 3 persons or entities will be used. Gradation of relationship will use the following terminology: Not related, probably not related, possibly related, probably related or definitely related.

8.51 Monitoring of Safety Data by the Protocol Team and the Study Monitoring Committee (SMC)

Since Phase I studies are not routinely reviewed by a Data and Safety Monitoring Board (DSMB), it is the responsibility of the protocol team to interpret safety data, and make decisions regarding SADRs that are needed to protect participants from undue risk.

The safety and tolerability of the study agent will be monitored by means of adverse events reports and toxicity reports presenting laboratory and clinical events. It is required that the data required for the toxicity reports be entered into the database within 72 hours of the time at which the results of the laboratory tests or clinical examinations become available.

Reports compiled by the Data Management Center (DMC) will be reviewed and discussed by the Protocol Team on conference calls held at least every 4 weeks. Data on accrual, pharmacokinetics and toxicity will be reviewed.

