- at least 3 of the first 8 participants to be included in the Cohort 2 RAL-unexposed group interim analysis have had treatment discontinuation due to non-life threatening Grade 3 or 4 severity SADR, judged to be at least possibly treatment related;

OR

- if after the Cohort 2 RAL-unexposed group interim analysis,
 - there was no dose adjustment and at least 6 of 20 participants to be included in Cohort 2 final analysis have had treatment discontinuation due to non-life threatening Grade 3 or 4 severity SADR, judged to be at least possibly treatment related; or
 - there was a dose adjustment and at least 4 of the 12 participants on the final dose for Cohort 2 have had treatment discontinuation due to non-life threatening Grade 3 or 4 severity SADR, judged to be at least possibly treatment related.

Following any temporary suspension of accrual, the team will further review the safety data within 48 hours of notification of the event to determine if continuation of accrual is appropriate. If the team, including the study chair, the DAIDS medical officer of record and Merck representatives, agrees that the study drug is likely to be safe for additional participants, they may decide to allow accrual to resume. However, the P1110 SMC will be informed of this decision, and the study will not reopen without the approval of this committee. The SMC may ask for any data it may want to review before making its decision. Regulatory agencies will be notified of the event and the team's and SMC's decision.

8.521 Final Evaluation of Cohort 1 Safety Data

At final evaluation of the Cohort 1 RAL-exposed or RAL-naïve groups, safety guidelines will be assessed on infants on the final dose for each group in Cohort 1 using safety data through week 6 of life. If none of the participants has experienced a new life-threatening event or death judged to be an SADR or a new Grade 4 event that is probably or definitely attributable to the study medication; and no more than 25% of the participants have had treatment discontinuation due to non-life threatening Grade 3 or 4 severity SADR at least possibly related to the study drug, then final dose in Cohort 1 has passed the safety guidelines. Otherwise the team will review the

safety data and will consult with the P1110 SMC to determine whether it is safe to proceed to Cohort 2 and under what conditions this will be allowed to occur.

8.522 Interim Evaluation of Cohort 2 RAL-naïve Group Safety Data

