The safety and PK of the starting dose for Cohort 2 will be assessed on the first 8 participants based on safety data through 6 weeks of life, for the purpose of determining whether accrual to the full cohort can proceed and determining if any adjustment in dosing may be necessary (see Section 9.0 for PK evaluation.). Accrual will be stopped while this interim analysis is being performed. Dosing decisions will depend upon severity of adverse events, attribution of these events to the study drug and PK data.

If none of the 8 participants has experienced a new life-threatening event or death judged to be an SADR or a new Grade 4 event that is probably or definitely attributable to the study medication; and no more than 2 of the participants have had treatment discontinuation due to non-life threatening Grade 3 or 4 severity SADR at least possibly treatment related to the study drug, then full accrual to Cohort 2 can proceed. Otherwise the team will review the safety data and will consult with the P1110 SMC to determine whether it is safe to complete full enrollment into Cohort 2 and under what conditions this will be allowed to occur.

8.523 Final Evaluation of Cohort 2 Safety Data

The safety guidelines will be assessed on the final dose for each group in Cohort 2 based on safety data through week 6 of life. If none of the participants has experienced a new life-threatening event or death judged to be an SADR or a new Grade 4 event that is probably or definitely attributable to the study medication and no more than 25% of the participants on the final dose for Cohort 2 have had treatment discontinuation due to non-life threatening Grade 3 or 4 severity SADR at least possibly treatment related to the study drug, then final dose in Cohort 2 has passed the safety guidelines.

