Safety data will include death, signs/symptoms, diagnoses and laboratory test results, which will include results of evaluations specified in the protocol and results from the infant's clinical care. Infants will be evaluable for safety analysis if they received at least one dose of RAL. The safety analyses for the final SDAC reports will be based on data on all safety evaluable infants, regardless of whether they are evaluable for PK analysis.

Under protocol Version 1.0, the following describes the safety monitoring for dose finding purposes:

- the team will monitor RAL safety during the regular team monitoring as specified in Protocol Section 8.52; and
- the assessment of the safety guidelines will be performed at full accrual to Cohort 1 (Protocol Section 8.521), at interim analysis when 8 participants have been accrued to Cohort 2 RAL-naïve group (Protocol Section 8.522) and at full accrual to Cohort 2 RAL-naïve group (Protocol Section 8.523).

For dose finding purposes, infants who have been excluded from the PK analyses due to evidence of problematic exposure to the study medication, will also be excluded from evaluation of the safety guidelines.

Infants will be followed for 24 weeks after birth. Women will be followed until discharge from the labor and delivery unit.

PRIMARY OBJECTIVES:

1. To evaluate the safety and tolerability through 6 weeks of life of RAL oral granules for suspension when administered during the first 6 weeks of life with standard PMTCT ARV prophylaxis to HIV-1 exposed infants assessed at high risk of HIV infection.
2. To evaluate the PK of RAL oral granules for suspension during the first 6 weeks of life along with standard PMTCT ARV prophylaxis.
3. To determine an appropriate dose of RAL oral granules for suspension for use in neonates and infants during the first 6 weeks of life.

SECONDARY OBJECTIVES:

1. To assess safety and tolerability of RAL oral granules for suspension through 24 weeks of life when administered during the first 6 weeks of life with standard PMTCT ARV prophylaxis to HIV-1 exposed infants assessed at high risk of HIV infection.

2. To investigate the relationship between neonatal RAL elimination and UGT1A1 genotype, and to determine whether there is an association of UGT1A1 (*28/*28) and SLCO1B3 (rs2117032-C/T) with hyperbilirubinemia.

3 Protocol Team Roster

4 Outline of Planned Analysis

This section contains the details of the analyses for:

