- interim and full cohort accrual safety reports: at full accrual to Cohort 1, at interim analysis when 8 participants have been accrued to Cohort 2 (safety analysis only) and at full accrual to Cohort 2 RAL-naïve group; and
- SDAC final reports: the first report will focus on Cohort 1 (both RAL naïve and exposed groups) and Cohort 2 RAL naïve group. Should protocol Version 2.0 be approved and Cohort 2 RAL-exposed group be opened to accrual, a second report will be generated at study closure to follow-up for Cohort 2 (both RAL naïve and exposed groups).

When applicable, separate summary tables will be generated for the women and their infants. Separate summary tables will be generated for each cohort since Cohort 1 neonates will receive two single RAL dosing while Cohort 2 neonates will receive daily RAL dosing through 6 weeks of life. Summary statistics for subgroups of infants will be provided alongside the overall cohort summary statistics. Infant subgroups will be defined in terms of infant in utero RAL exposure and RAL dosing. For Cohort 1, there are 3 infant subgroups: (i) RAL-naïve (3mg/kg-3mg/kg), (ii) RAL-naïve (2mg/kg-3mg/kg), and (iii) RAL-exposed (1.5mg/kg-3mg/kg). Cohort 2 RAL-naïve group only has one dosing which was specified in **Section 2**.

The interim and full cohort accrual safety reports will be prepared for the core team and, if necessary, for the SMC. These reports will include information concerning Screening and Entry, Participant and Study Status, Baseline, and Safety summary tables. Unless otherwise noted the SDAC final reports will contain all summary tables.

Additional participant listings necessary in writing up the SDAC final report will be generated and will be used internally at SDAC. Highlights of these listings will be included in the SDAC final report. These participant listings will be provided to the manuscript writing team. The manuscript writing team, which is a subset of the protocol team, will be identified by the protocol team.

The analysis of the PK data will be performed by the protocol pharmacologists and thus, not included in this document.

Validation requirements as per SDAC SOPs will be as follows:

- a. All dataset creation programs will be validated with double coding for the primary and secondary safety endpoints.
- b. All study-specific formats will be validated.
- c. Validation of analysis programs is specified in the following subsections.

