4.7 Safety Analysis for Dose Finding and Possible Early Study Discontinuation

Purpose:

To list the endpoints and summary tables of safety analysis for dose finding and possible early study discontinuation. Reports will be generated at full accrual to cohort 1 and at interim and full accrual to cohort 2.

Analysis Program Validation:

Code review required. Primary analysis will require double coding.

Data:

Infant Safety Data are adverse clinical and laboratory events reported in Hematology and Liver Chemistries ((LBW0093), Signs/Symptoms (PE6831), Diagnosis (PE6852) and Death (PE1414) CRFs. (The following variables in the SDAC SAS datasets will be used: EVENTDSC, EVNGRDE, FORMNM and FORMTYP in EVENTS table; TRACKCD and RELATSP in TRAC table; and RAL1ST, RAL1RS, RAL2ST, RAL2RS in TXW0276 CRF).

Analysis:

Infants who have been excluded from the PK analyses, due to evidence of problematic exposure to the study medication, will be excluded from evaluation of the safety guidelines. AEs and SADRs will exclude events classified by the team as “baseline” or “ongoing baseline” events.

- a) Safety endpoints for Cohorts 1 and 2 in dose finding and possible early study discontinuation
 - Safety endpoints
 - based on data through 6 weeks (i.e. through 49 days) of life:
 - i. Life threatening event or death judged to be a SADR or Grade 4 event that is judged to be probably or definitely attributable to the study medication
 - ii. Treatment discontinuation due to non-life threatening Grade 3 or 4 severity SADR, judged to be at least possibly treatment related

Notes: During the regular monitoring, the team will assess whether an AE is life threatening and the assessment will be entered in the TRAC table. Treatment discontinuation due to an AE will be on the TXW0276 CRF.

- b) Summary table for the interim and cohort full accrual safety reports (analysis for dose finding and possible early study discontinuation).
Note: Only the overall summary will be provided since we are expecting very few infants meeting the safety endpoint.

Table: Summary table showing number (%) of the proportion of infants who meet the safety endpoints for dose finding and possible early study discontinuation.

Table 7: Summary of Infants Meeting the Safety Endpoints for Dose Finding and Possible Early Study Discontinuation

Endpoint	Number and Proportion

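### SAP 4.7 tabulates the safety guidelines for the whole cohort only, although the protocol assesses them by exposure group, so no specified table applies the 25% limit to the Cohort 2 RAL-exposed group

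*SAP*

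**What the plan says.** **Protocol.** For Cohort 1, section 8.521 states that "safety guidelines will be assessed on infants on the final dose for each group in Cohort 1". For Cohort 2, section 8.523 states: "The safety guidelines will be assessed on the final dose for each group in Cohort 2". Both sections have two limbs. No infant may have a life-threatening or fatal SADR, or a Grade 4 event probably or definitely due to the drug. In addition, at most 25% may have stopped treatment for a non-life-threatening Grade 3 or 4 SADR. Section 8.523 is not uniform: it opens with each group, but the clause that carries the 25% limit then refers to Cohort 2 without naming groups.

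**SAP, level of summary.** The general convention in SAP section 4 is: "Summary statistics for subgroups of infants will be provided alongside the overall cohort summary statistics". SAP 4.7 departs from it: "Only the overall summary will be provided since we are expecting very few infants meeting the safety endpoint". Table 7 accordingly has a single column for number and proportion.

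**SAP, timing.** SAP section 2, in a list introduced as applying under protocol Version 1.0, places the last guideline assessment "at full accrual to Cohort 2 RAL-naïve group (Protocol Section 8.523". SAP section 4 also names only the RAL-naïve group for the Cohort 2 full-accrual safety report. SAP 4.7 names no exposure group: "Reports will be generated at full accrual to cohort 1 and at interim and full accrual to cohort 2". Protocol 8.5 is equally general: "at interim analysis when 8 participants have been accrued to Cohort 2 and at full accrual to Cohort 2". If Version 2.0 is approved, SAP section 4 adds a final report: "a second report will be generated at study closure to follow-up for Cohort 2 (both RAL naïve and exposed groups". It adds no guideline assessment to go with it.

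**The concern.** A rule defined for each group needs a table with a row or column for each group. Table 7 is the only table the SAP specifies for the guideline limbs, and it does not have that form. The reason given, that few events are expected, does not support pooling: when events are few, two or three in a small group decide whether that group is over 25%.

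The group at stake is Cohort 2 RAL-exposed, the only one still to be enrolled. The accrual-suspension counts in Protocol 8.52 do not cover it separately. The first discontinuation count for Cohort 2 (3 of the first 8) is tied to the RAL-unexposed interim analysis. The later ones are 6 of 20 in the Cohort 2 final analysis, or 4 of 12 after a dose adjustment. Section 8.523 is therefore the only place where the 25% limit is applied to this group on its own.

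**Working it through.** **Inputs**
- Limit: at most 25% discontinued (Protocol 8.523).
- RAL-exposed group: minimum 8 (Protocol 8.4).
- RAL-naïve group: 26 accrued (SAP section 2). Infants excluded from PK analysis for problematic exposure also leave the guideline denominator, so I also use 20, the Cohort 2 PK-evaluable minimum, as an assumed lower figure.

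**1. How the plan turns 25% into a count.** Take the limit as c = floor(0.25n). With p the discontinuation rate and q the rate of the severe events, the probability of failing is 1 − Σ(x = 0 to c) C(n,x) p^x (1−p−q)^(n−x). At n = 8, c = 2, p = 0.25, q = 0:

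1 − (0.75^8 + 8·0.25·0.75^7 + 28·0.25²·0.75^6) = 1 − (0.10011 + 0.26697 + 0.31146) = 0.321

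Table 12 prints 0.32. At n = 20, c = 5, the same rates give 0.383, and Table 13 prints 0.38. The count rule is therefore the plan's own.

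**2. Limits by level**

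| Set | n | Largest passing count | First failing count |
|---|---|---|---|
| RAL-exposed alone | 8 | 2 | 3 (37.5%) |
| Pooled with 20 naïve | 28 | 7 | 8 (28.6%) |
| Pooled with 26 naïve | 34 | 8 | 9 (26.5%) |

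**3. Which report would contain the RAL-exposed infants?** There are two readings.
- *SAP sections 2 and 4.* The Cohort 2 full-accrual report covers the RAL-naïve group. That group has one regimen, so overall and group are the same and Table 7 is correct for it. The RAL-exposed group has no named guideline report.
- *SAP 4.7 taken literally.* The report comes at full accrual of Cohort 2 and gives the overall figure only. Once the RAL-exposed group is enrolled, the two groups are pooled.

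**4. What Table 7 would show on the second reading.** Take 3 of 8 exposed infants discontinued and no RAL-naïve discontinuations:
- with 20 naïve, 3/28 = 10.7%;
- with 26 naïve, 3/34 = 8.8%;
- if the cohort minimum of 20 is taken to include the 8 exposed infants (12 naïve), 3/20 = 15.0%.

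All three are under 25%. The result does not need zero naïve events: with 4 of 20 naïve the pooled figure is 7/28 = 25.0%, and with 5 of 26 it is 8/34 = 23.5%. Neither exceeds the limit.

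**5. The zero-event limb.** One qualifying event in either group makes the pooled count non-zero, so pooling cannot hide a failure of this limb. It hides only the group in which the event arose.

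**The case against.** **Sequencing.** SAP V3.0 is dated 3 January 2017 and protocol Version 2.0 is dated 18 January 2017. The list in SAP section 2 is confined to Version 1.0, and the SAP says that it may be modified. A missing report for a group not yet approved is largely an expected update. This stands. It does not explain the overall-only note, which conflicts with 8.521 and 8.523 whatever the version order.

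**No document sets out a 28- or 34-infant table.** True. The pooled percentages hold only on the literal reading of SAP 4.7. On the other reading, the gap is an unnamed report and not a misleading figure.

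**The rule belongs to the protocol, and practice looks group-wise.** Protocol 1.29 reports the guidelines as met for the Cohort 2 RAL-naïve infants, and SAP section 2 cites 8.521 to 8.523 by number. This makes a pooled pass/fail decision less likely, but the specified table still does not supply what a group-wise decision needs.

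**Other safeguards.** Grade 3 or 4 SADRs reach the team within 24 hours (Protocol 6.11), and the team reviews data at least every 4 weeks (8.5). The guideline reports include off-treatment reasons (SAP 4.3). SAP 4.6 gives Grade 3 or 4 SADRs by subgroup with 90% intervals in the final report. Three discontinuations of this kind should appear there as at least three SADRs in the RAL-exposed column, subject to differences in attribution source. These limit the harm, but none applies the 25% limit by group, and the SAP 4.6 tables come only at closure of follow-up.

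**Stronger readings to avoid.** A reader might infer that a failing RAL-exposed dose would probably be passed. The documents do not support this, because the chance depends on discontinuation rates that they do not give. If both groups share one rate (1% to 60% examined), the chance that the exposed group exceeds its limit while the pooled figure does not is at most 0.12, even ignoring the accrual-suspension counts. A reader might also infer that the Cohort 1 dose decision was compromised. The documents give no event counts to show that, and Cohort 1 is closed.

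**Conclusion.** The mismatch stands as a minor point. The protocol assesses the guidelines by exposure group on the final dose. The SAP's table for them is overall only, without a final-dose restriction, and contrary to the SAP's own convention. The RAL-naïve full-accrual report is not affected. For the Cohort 2 RAL-exposed group, the SAP offers either no named guideline report or, read literally, one in which 37.5% could appear as roughly 9% to 11%. Those percentages rest on 8 exposed infants, on 20 or 26 RAL-naïve infants in the denominator, on no RAL-naïve discontinuations, and on the literal reading of SAP 4.7. The conflict in level of summary does not depend on any of these. The protocol contributes some ambiguity, since the 25% clause in 8.523 does not repeat the reference to groups.

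**What to change.** 1. In SAP 4.7, replace the overall-only note. Produce Table 7 by exposure group, restricted to infants on that group's final dose, with denominators, beside the overall column.
2. At the next SAP revision, name a guideline report at full accrual of the Cohort 2 RAL-exposed group, and bring SAP sections 2 and 4 into line with SAP 4.7.
3. In Protocol 8.523, reconcile the opening reference to each group with the later reference to Cohort 2. A table with both group and overall columns serves whichever meaning the team confirms.

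The cost is extra columns in one table, one named report, and a wording change in one protocol section. No additional infants or data are needed, the 25% limit is unchanged, and nothing has to be redone for Cohort 1.

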4.8 Infant Infection Testing

Purpose:

To describe the infant HIV infection status.

Analysis Program Validation:

Not required.

Data:

INFECT2 table holds the infection status of the participants while on study follow-up. Site assessment of infant infection status will be in INFECT2. HIV DNA test results will be in DNALDMS, and HIV RNA results will be in L_RNAFIN and F3109.

Analysis:

Table: Tabulation of infection status of the infants from the INFECT2 table.

4.9 Genotype Analysis

Purpose:

To list the tables for investigating the relationship between neonatal RAL elimination (as reflected in CL/F) and UGT1A-1 genotype, and the relationship between UGT1A-1 and SLCO1B3 with hyperbilirubinemia.

Analysis Program Validation:

Code review required.

Data:

HUMGENO table and LBW0093 CRF (TBILCV, BILPHOTO, BILTRANS, BILOTH and BILOTHSP).

Analysis:

- a) Response variables for genotype analysis:
 - UGT1A-1 genotype (presence or absence of *28/*28 genetic variant):
Wild-type: (TA)₆(TA)₆; mutation: (TA)₅(TA)₆, (TA)₆(TA)₇ and (TA)₇(TA)₇
 - SLCO1B3 (rs2117032-C/T) genotype:
C/C, C/T and T/T
 - Hyperbilirubinemia defined as total bilirubin exceeding 16.0 mg/dL or infant requiring exchange transfusion for hyperbilirubinemia

b) Output tables:

Table: Summary descriptive statistics (N, geometric mean, median, 25th and 75th percentiles, min, and max) on CL/F will be generated for the subgroups of participants depending on whether they exhibit the UGT1A1 polymorphism.

Table 8: Summary of Infant RAL CL/F between UGT1A1 Genotype Groups for Cohort 1 (mock-up table)

		UGT1A1 Genotypes					Overall	p-value ^a for all genotypes	p-value ^b for wild-type vs. mutation
		Wild-type	Mutation			Overall			
		(TA)6(TA)6	(TA)5(TA)6	(TA)6(TA)7	(TA)7(TA)7				
CL/F of RAL-naïve Infants	N								
	mean								
	median								
	...								
CL/F of RAL-Exposed Infants	N								
	mean								
	median								
	...								
CL/F of All Infants	N								
	mean								
	median								
	...								

a Comparison of median among different genotypes will use Kruskal–Wallis test for CL/F of all infants only. The formal comparison will be done only if we have enough infants in the listed genotype groups.

b Comparison of median between wild-type vs. mutation will use Wilcoxon Rank Sum Test for CL/F of all infants only. The formal comparison will be done only if we have enough infants in the listed genotype groups.

**Table 9: Summary of Infant RAL CL/F between UGT1A1 Genotype Groups for Cohort 2
(mock-up table)**

		UGT1A1 Genotypes					Overall
		Wild-type	Mutation			Overall	
		(TA)6(TA)6	(TA)5(TA)6	(TA)6(TA)7	(TA)7(TA)7		
CL/F from the 1st intensive PK analysis	N						
	mean						
	median						
	...						
CL/F from the 2nd intensive PK analysis	N						
	mean						
	median						
	...						

Note: This table is for Cohort 2 RAL-naïve group only and should we have data on Cohort 2 RAL-exposed group, additional columns for: (i) RAL-exposed group, and (ii) Overall Cohort 2, will be added. Formal comparisons for all Cohort 2 infants will be done by then.

Table: Association between UGT1A-1 genotypes and hyperbilirubinemia (yes/no) with Fisher’s Exact Test.

Table 10: Summary of Cohort 1 Infant Hyperbilirubinemia between UGT1A1 Genotype Groups (mock-up table)

Characteristic		Wild-type	Mutation				Overall (N=0)	P-value* for all genotype groups	P-value* for Wild-type vs. Mutation
		(TA)6(TA)6	(TA)5(TA)6	(TA)6(TA)7	(TA)7(TA)7	Overall			
Hyperbilirubinemia	Yes	0	0	0	0	0	0.000	0.000	
	No	0	0	0	0	0			

*Fisher’s Exact Test. The power of test will depend upon the distributions of the variables to be analyzed, but will be extremely limited due to the small sample size.
Note: Similar table will be created for Cohort 2 infants.

Table: Association between SLCO1B3 genotypes and hyperbilirubinemia (yes/no) with Fisher’s Exact Test.

Table 11: Summary of Cohort 1 Infant Hyperbilirubinemia among SLCO1B3 Genotype Groups (mock-up table)

Characteristic		C/C (N=0)	C/T (N=0)	T/T (N=0)	Total (N=0)	P-Value*
Hyperbilirubinemia	Yes	0	0	0	0	0.000
	No	0	0	0	0	

*Fisher’s Exact Test. The power of test will depend upon the distributions of the variables to be analyzed, but will be extremely limited due to the small sample size.
Note: Similar table will be created for Cohort 2 infants.
